AFRS

	1	
	BID	Twice a day
	CFR	Code of Federal Regulations
	CRSwNP	Chronic Rhinosinusitis with nasal polyps
	CT	Computed tomography
	EDC	Electronic Data Capture
	FU	Follow-up
	GCP	Good clinical practice
	ICF	Informed consent form
	IMP	Investigational medicinal product
	INCS	Intranasal corticosteroids
	IP	Investigational product
	IPD	IP discontinuation
	IRB	Institutional Review Board
	LMS	Lund-Mackay score
	mLK	Modified Lund Kennedy Endoscopic Score
	SNOT-22	SinoNasal Outcome Test, 22 item
	SoC	Standard of Care
	WOCBP	Women of childbearing potential
Funding	Sanofi	
Source		

Schema

2. Background

Allergic fungal rhinosinusitis (AFRS) is a severe form of eosinophilic nasal polyposis with critically inadequate treatment options for the 10% of chronic rhinosinusitis participants affected by the disease. Occlusive eosinophilic mucus and severe nasal polyposis presents in early adulthood, with an unrelenting course marked by sinus expansion and pressure-induced dehiscence of the surrounding orbit and skull base. Despite appropriate therapies with oral/topical corticosteroids, saline irrigations and comprehensive sinus surgery, nasal polyps aggressively recur, frequently within months of surgery. Medical options beyond topical and systemic steroids are limited. Neither antifungal nor allergen immunotherapy are beneficial. Due to persistent sinonasal inflammation, patients with AFRS receive an average of three corticosteroid bursts per year and revision sinus surgery every 42 months.

Rationale

In addition to the activation of type 2 inflammatory mediators found in other CRSwNP phenotypes, AFRS is uniquely characterized by an exaggerated activation of the adaptive immune response with serum IgE levels often above 1000 kU/L and defined by an upregulation of fungal specific IgE levels [1]. Marked eosinophilic inflammation is found throughout the upper airway, and the degree of mucosal eosinophil infiltration has been repeatedly reported as a potent predictor of poor surgical outcomes. We therefore hypothesize that dupilumab, a human monoclonal antibody that targets the type-2 inflammatory cascade, is a safe and effective treatment for nasal polyps as add-on therapy following endoscopic sinus surgery.

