3.1 Primary Objectives

on initially objectives				
Co-Primary objectives	Endpoint/variable(s)			
	Change from baseline at 52 weeks both within			
	and between treatment and placebo arms			
Determine the efficacy of dupilumab in	Endoscopic modified Lund-Kennedy			
controlling sinonasal inflammation and	(mLK) score			
preventing nasal polyp recurrence after				
complete sinus surgery for AFRS				
 Evaluate the effect of dupilumab on 	• Incidence of oral corticosteroid utilization			
oral corticosteroid utilization following	per participant			
complete sinus surgery for AFRS				

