4.1 Overall Design

This is a multi-center, randomized, double-blinded, placebo-controlled, parallel group study to evaluate the efficacy of dupilumab 300mg administered subcutaneously (SC) every 2 weeks versus placebo in participants with AFRS following planned sinus surgery.

132 participants will be randomized to receive dupilumab 300mg SC or matching placebo while on a background of intranasal corticosteroid sprays twice daily. Patients will be stratified by study site and by baseline comorbid asthma status (yes vs no). ~25% of the randomized participants will have comorbid asthma.

Eligible participants will enter a screening/run-in period on twice daily nasal saline irrigations followed by INCS spray for 2-6 weeks prior to planned sinus surgery. Participants may be consented and enrolled at any time during this 2-6 week run-in period, provided the failure of appropriate medical therapy has been documented as outlined in the inclusion criteria. Eligible participants already on study background therapy for at least two weeks may be consented and enrolled during the pre-surgery period.

Both saline irrigations/INCS and sinus surgery will be completed per standard of care (SoC) and not according to the study protocol. Patients who continue to meet eligibility criteria following surgery will be randomized 1:1 before Visit 3 (Day 0) when they receive placebo or dupilumab 300mg SC every 2 weeks. Patients will receive a total of 26 doses of IMP, via either study

personnel (Visit 3-6 at W0, 12, 24 and 36) or home-administration (W2, 4, 6, 8, 10, 14, 16, 18, 20, 22, 26, 28, 30, 32, 34, 38, 40, 42, 44, 46, 48, 50) to maintain a 2-week treatment schedule. Patient compliance will be recorded via text messages the day of scheduled home administration, as well as monthly phone calls and collection of used syringes during scheduled study visits (Visit 4-7 at W12, 24, 36 and 52). An EOT visit will be conducted at Week 52 (Visit 7). Patients will then be monitored on daily saline irrigation and INCS spray for 12-weeks to evaluate potential disease recurrence after discontinuation of IMP. An EOS visit will be conducted at Week 64 (Visit 8).

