14.6 Primary Analysis

To examine changes in the co-primary outcomes, the modified Lund-Kennedy score and the incidence of oral corticosteroid utilization per participant, a mixed effects longitudinal model will be fit that includes group (dupilumab, placebo) as a between participants factor and time (randomization through post-treatment period) as a categorical within participants factor plus their interaction term. Time is treated as categorical so that we can use the group-time interactions with the time main effect to estimate and test intent-to-treat (ITT) group differences at each time point, with 52 weeks as our primary ITT test. As randomization is stratified by site, site will also be included in the model. This mixed effects model allows incorporation of a random intercept term for each subject, different numbers of measurements (in case a visit is skipped), and the choice of appropriate variance-covariance structure. The mixed model will also permit identification of any significant changes in the post-treatment period from 52 to 64 weeks. This primary mixed model will incorporate all subject's randomized.

The primary objective will be assessed by testing this null hypothesis: treatment with Dupilumab post-surgery is equivalent to treatment with placebo post-surgery at 52-week end of treatment. The additional time point at 64 weeks is included in the model to ensure efficient evaluation of both co-primary outcomes at the EOT and 12 weeks after EOT. Significant changes between weeks 52 and 64 will be examined by linear contrast. We will test the following null hypotheses against two-sided alternatives:

- H₀₁: there is a lack of difference between the changes in mLK from baseline to 52 weeks and from baseline to 64 weeks for the untreated.
- H_{02} : there is a lack of difference between the changes in mLK from baseline to 52 weeks and from baseline to 64 weeks for the treated.
- H_{03} : the treatment effect dissipates between 52 and 64 weeks.

The primary estimand for the primary endpoint is the composite/treatment policy strategy. The intercurrent events will be handled as follows:

- Undergoing sinus surgery for AFRS: data after surgery will be assigned the worst possible score (composite strategy)
- Taking SCS or other rescue medications: data collected after use will be used in the analysis (treatment policy strategy)

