14.7 Secondary and Exploratory analyses

In a secondary analysis, a similar mixed model as described above will be fit that includes the subset of participants who are receiving treatment (dupilumab or placebo) for both nostrils. This model will incorporate nesting factors to identify repeated measures by subject and by nostril.

In an exploratory analysis, we will also compare the proportion of participants whose modified Lund- Kennedy score improved by greater than or equal to 2 units. For participants who undergo sinus surgery for AFRS prior to Week 52, non-responder imputation will be used. We will utilize a Chi-square or Fisher's exact test to examine if this proportion is significantly different by treatment group (dupilumab or placebo) at 52 weeks.

For the continuous secondary outcomes (e.g. SNOT-22 score, NPS, FEV1), a mixed effects longitudinal model will be fit that includes group (dupilumab, placebo), time (randomization through post-treatment period), and their interaction term in a similar fashioned as described for the primary outcome modified Lund-Kennedy score. For the secondary outcomes that compare the number of participants requiring rescue treatment and the number of adverse events (safety) over 52 weeks, similar mixed effects models will be fit but with consideration of a Poisson distribution (as opposed to normal distribution). The mixed effects models for both primary and secondary outcomes will permit the inclusion of any significant potential confounders.

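### The Week 52 to 64 contrast is not interpretable for oral corticosteroid use: the per-visit variable has no counting window or time denominator, and the two intervals are 16 and 12 weeks

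*Combined protocol and SAP*

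**What the plan says.** - **Endpoint.** Section 3.1 defines the second co-primary as "Incidence of oral corticosteroid utilization" per participant. It gives no window, unit of time or rule for what is counted.
- **Model.** Section 14.6 covers both co-primaries at once: "a mixed effects longitudinal model will be fit that includes group (dupilumab, placebo) as a between participants factor", with time as a categorical within-participant factor running through the post-treatment period. No distribution or exposure term is given for OCS use.
- **Week 64.** Section 14.6 states: "The additional time point at 64 weeks is included in the model to ensure efficient evaluation of both co-primary outcomes at the EOT" (Week 64 itself is named next). The next sentence but no other text describes the comparison: "Significant changes between weeks 52 and 64 will be examined by linear contrast". It names no outcome.
- **Hypotheses.** H01 and H02 concern mLK ("there is a lack of difference between the changes in mLK from baseline to 52 weeks" and to 64 weeks, by arm). H03, on whether the treatment effect dissipates, names no outcome. The end-of-treatment to end-of-study objectives in section 3.2 list mLK, NPS, SNOT-22 and ACQ, not OCS use.
- **Visits.** Table 1 and section 4.1 place visits at Weeks 0, 12, 24, 36, 52 and 64.
- **Data.** Section 4.7.3 records start and end dates of all medications.

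**The concern.** A visit contrast compares like with like only if the variable means the same thing at both visits. An mLK score does. A number of steroid courses depends on how long the participant was observed, and the visit spacing changes exactly where the contrast is taken.

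Sections 4.1 and 4.2 give the 12-week off-drug period the purpose of showing durability or recurrence after stopping IMP. If the OCS contrast is run as written, calendar spacing is mixed with any real change in steroid use. Depending on how the value is coded, a stable rate could be reported as improvement or as worsening after stopping. On an additive scale, a stable treatment effect could be reported as fading.

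**Working it through.** **The plan's own figure.** The documents give no number for the OCS outcome or for this contrast. The one sample-size figure (section 14.1: 66 per group, 90% power, mLK difference 2, SD 3.5, two-sided 0.05) reproduces: 65 per group by the normal approximation, and 90.3% power at 66 by the noncentral t. It says nothing about OCS.

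**Interval lengths (Table 1).**
- Week 36 to 52: D364 − D252 = 112 days = 16 weeks.
- Week 52 to 64: D448 − D364 = 84 days = 12 weeks.

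**Apparent change when the true rate is constant.**

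| What the visit value is | Week 64 / Week 52 | Apparent change |
|---|---|---|
| Courses since previous visit | 12/16 = 0.75 | −25% |
| Any course since previous visit, 3/year | 0.500/0.603 = 0.83 | −17% |
| Any course since previous visit, 1/year | 0.206/0.265 = 0.78 | −22% |
| Cumulative courses | 64/52 = 1.23 | +23% |
| Courses per week observed | 1.00 | none |

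The yes/no rows use 1 − exp(−rate × weeks/52). With ±7 days at each of the three visits (Table 1), one participant's interval ratio can run from 70/126 = 0.56 to 98/98 = 1.00, so nominal weeks are not an adequate denominator either.

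**False signals on the interval-count reading.** For illustration, section 2 says "patients with AFRS receive an average of three corticosteroid bursts per year". At that rate the expected counts are 3 × 16/52 = 0.923 and 3 × 12/52 = 0.692, a difference of 0.231. With independent Poisson counts and n = 66, SE = √((0.923 + 0.692)/66) = 0.156, z = 1.48, and the rejection probability is about 31%.

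Simulation (20,000 trials, 66 in one arm, gamma-Poisson counts with shape 1, paired t-test, complete data, constant rate):

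| Courses/year | Rejection at 0.05 | Rejection at 0.05/3 | At 0.05, scaled for time |
|---|---|---|---|
| 0.5 | 8% | 3% | 5% |
| 1 | 13% | 5% | 5% |
| 2 | 21% | 10% | 5% |
| 3 | 29% | 15% | 5% |

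Nearly all unscaled rejections are falls. The 0.05/3 column applies the Bonferroni correction of section 14.6 to the three listed nulls; the section does not define the family, so the divisor is an assumption.

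**A real rebound.** Apparent ratio = 0.75 × true rate ratio. A true ratio of 1.33 shows as 1.00, 1.5 as 1.13 and 2.0 as 1.50. At 3/year and 0.05, a ratio of 1.5 is detected as a rise in about 10% of trials unscaled against 58% scaled; a ratio of 2.0 in about 67% against 98%.

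**Between arms.** With constant rates of 3 and 1 per year, the additive difference is 2 × 16/52 = 0.615 at Week 52 and 2 × 12/52 = 0.462 at Week 64, a 25% shrinkage. An additive arm-by-time test then rejects in about 13% of trials (9% for 3 versus 1.5, 8% for 2 versus 1, 6% for 1 versus 0.5). The rate ratio is 1/3 in both intervals, so a log-link model shows no distortion.

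**Cumulative reading.** The Week 64 value cannot be below the Week 52 value. At 3/year it moves from 3.00 to 3.69 with no change in rate, so the contrast is positive by construction.

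**The case against.** The strongest reply is that the plan never says a 16-week count will be set against a 12-week count. The per-visit OCS variable is simply undefined. If it were a rate, there would be no fault. This stands, and it is why the point concerns interpretability and not a bias of known sign. A reader might infer that the plan is tilted towards finding no recurrence; the documents do not support that, because the cumulative reading errs the other way.

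Second, an OCS contrast is less firmly planned than an mLK one. H01, H02 and the section 3.2 objectives omit OCS. This softens the point but does not remove it: section 14.6 keeps Week 64 for both co-primaries and the contrast sentence that follows has no restriction.

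Third, the false-signal rates depend on assumptions. The section 2 figure describes the disease in general, not post-operative participants on trial, and Bonferroni roughly halves the rates or better. Both are fair, and the ranges above reflect them. Pooling the arms would give larger rates, but no listed hypothesis pools them.

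Fourth, a reader might extend the fault to section 14.7, where for rescue use and adverse events "similar mixed effects models will be fit but with consideration of a Poisson distribution". That does not follow. Those outcomes are stated over 52 weeks, no Week 64 comparison of them is described, and on a log scale a common window factor cancels between arms.

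**Conclusion.** The point holds in limited form. For OCS use, section 14.6 as written does not yield an interpretable Week 52 to 64 comparison: an unchanged rate appears as anything from −25% to +23% across the count readings, and only a rate, which the plan does not state, avoids this. The interval lengths and these ratios come directly from the visit schedule. The false-signal rates rest on the interval-count reading, the assumed course rates and overdispersion, and complete data.

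Two stronger conclusions are not supported. The between-arm test at Week 52 is not distorted by the 16 versus 12 week mismatch, because both arms share the same window. Nor is a rebound simply hidden: on the interval-count reading it is fully masked only up to a rate ratio of 1.33, and larger rebounds are attenuated but visible. The matter should be settled before analysis, since it affects the off-drug reading of a co-primary outcome and not its main test.

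**What to change.** In section 14.6:

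1. Limit the Week 52 to 64 linear contrast to mLK.
2. For OCS, define the variable as courses starting in each period, derived from the recorded medication dates.
3. Fit a count model (for example negative binomial or Poisson mixed) with log(weeks actually observed) as offset.
4. Report the off-treatment period (Weeks 52 to 64) against the on-treatment period as a rate ratio, within each arm, and compare these ratios between arms.

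Section 14.7 needs no change on this account.

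The cost is SAP wording; no new data or visits are needed. The drawback is that the OCS durability result becomes a rate ratio from a separate model, so it no longer sits beside mLK as a contrast from one common model.

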3.2 Secondary Objectives

Secondary objectives	Endpoint/variable(s)	
	Change from baseline at 52 weeks both within	
	and between treatment and placebo arms	
To evaluate the effect of dupilumab on:		
Prevention of revision surgery for AFRS	Prevalence of revision sinus surgery for recurrent nasal polyps, and comparison of survival curves	
Secondary objective measures of sinonasal	• Endoscopic nasal polyp score (NPS)	
inflammation following sinus surgery	CT generated Lund-MacKay score	
• Lower airway dysfunction following sinus surgery in the subgroup of participants with asthma (~25%)	Spirometry	
• Upper and lower airway, disease-specific,	• 22-item sinonasal outcomes test (SNOT-22)	
health-related quality of life	Asthma Control Questionnaire (ACQ)	
Reducing utilization of rescue medications for acute exacerbations of CRS following sinus surgery	 Prevalence of oral / topical corticosteroid utilization per treatment cohort Incidence of oral / topical antibiotic utilization per subject Prevalence of oral / topical antibiotic utilization per treatment cohort 	

Other secondary objectives	Endpoint/variable(s)
	Change from end of treatment (EOT) to end of

	study (EOS)
To evaluate the effect of dupilumab on:	
Objective measures of sinonasal	Endoscopic modified Lund-Kennedy
inflammation following sinus	(mLK) score
surgery	• Endoscopic nasal polyp score (NPS)
• Upper and lower airway, disease-specific,	• 22-item sinonasal outcomes test (SNOT-22)
health-related quality of life	Asthma Control Questionnaire (ACQ)

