4.2 Scientific Rationale for Study Design

This study is designed to evaluate the safety and efficacy of fixed dose dupilumab (300mg) administered SC every 2 weeks, on top of intranasal corticosteroid spray in participants undergoing sinus surgery for medically recalcitrant nasal polyps in AFRS. The population is composed of participants with ongoing chronic symptoms despite appropriate medical management who elect to undergo sinus surgery per SoC. The randomized, placebo- controlled design allows for determination of IMP efficacy in preventing recurrence of severe sinonasal disease.

The sample size (n=132) and 52-week treatment duration are appropriate to capture maintenance effects while providing 1-year treatment safety data in the intended study population. Following completion of the treatment phase, all participants will enter an additional 12-week observation period to demonstrate durability of response and provide off-treatment safety data.

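### H03 in section 14.6 is written as a null but asserts a loss of effect, so the literal decision on the off-treatment contrast is reversed

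*Combined protocol and SAP*

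**What the plan says.** Section 14.6 introduces its list with "We will test the following null hypotheses against two-sided alternatives". H01 (untreated) and H02 (treated) each state that the mLK change from baseline is the same at week 52 and week 64. H03 states that "the treatment effect dissipates between 52 and 64 weeks". It gives no amount and, unlike H01 and H02, does not name mLK.

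Just before the list, the section says "Significant changes between weeks 52 and 64 will be examined by linear contrast". Earlier it says that the model will "estimate and test intent-to-treat (ITT) group differences at each time point", with week 52 as the primary test.

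The off-treatment question is a stated aim elsewhere:
- The second table of section 3.2 includes mLK and sets its endpoints as "Change from end of treatment (EOT) to end of" study.
- Section 4.1 follows participants off drug "to evaluate potential disease recurrence after discontinuation of IMP".
- Section 4.2 describes a "12-week observation period to demonstrate durability of response and provide off-treatment safety data".

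On the responder analysis, section 14.7 compares the proportion whose mLK "score improved by greater than or equal to 2 units", labels this exploratory, and names no baseline visit. Section 5.2.1 treats a rise of at least 2 points from the postoperative score as clinically significant worsening. Section 14.10 expects the effect to appear as worsening on placebo.

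**The concern.** A two-sided test needs a null that fixes a value, normally zero change. H01 and H02 do this. H03 puts the finding of interest, loss of effect, where the no-change statement belongs. H03 is also the only listed hypothesis on whether the between-arm effect lasts after treatment stops, because H01 and H02 are within-arm. A significant change in one arm and a non-significant change in the other does not test the difference between arms, so they cannot stand in for it.

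At stake is the conclusion reported from the 12-week period. A literal reading gives a statement that contradicts the estimate. A non-significant contrast could also be reported as evidence of durability when the interval is too wide to show it.

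The exploratory responder rule raises a smaller question: it counts movement in the direction opposite to the one for which the protocol gives a clinical threshold.

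**Working it through.** **1. The plan's own figure.** Section 14.1 gives 66 per group, a 2-point difference, SD 3.5, two-sided 0.05 and 90% power. The normal approximation gives 65 per group for 90% power, and 90.7% power at 66. The noncentral t gives 90.3% at 66 and 89.9% at 65. The stated size reproduces.

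**2. What the three hypotheses should be.** Let T and P be the mean mLK scores on dupilumab and placebo, and D = T − P. Higher mLK is worse, so benefit is a negative D.
- H01: P64 − P52 = 0.
- H02: T64 − T52 = 0.
- The matching third null is the difference of these two: (T64 − T52) − (P64 − P52) = D64 − D52 = 0.

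This is a week 52-to-64 linear contrast and agrees with the change endpoint in 3.2.

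**3. What the literal wording does.** Take correlation 0.5 between weeks 52 and 64 (assumed), so that SE(D64 − D52) = 0.609 (step 4).
- Observed D52 = −2, D64 = 0 (effect gone): z = 2/0.609 = 3.28, p = 0.001. The listed null is rejected, so the literal conclusion is that the effect did not dissipate.
- Observed D52 = −2, D64 = −2 (effect fully kept): z = 0, p = 1.00. The listed null is retained, so the literal conclusion is that dissipation stands.

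Both statements contradict the data. Treating H03 as a directional null (any loss at all) would make the test one-sided, against the two-sided alternatives stated for the list.

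**4. Precision of the corrected contrast.** Assumptions beyond the documents: SD 3.5 also at week 64, no dropout, correlation r from 0.3 to 0.9, and 0.05 before any Bonferroni correction.

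SE(D64) = 3.5 × √(2/66) = 0.609; half-width 1.96 × 0.609 = 1.19.

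SE(D64 − D52) = 3.5 × √(2(1 − r)) × √(2/66). Power for a loss of d is approximately Φ(d/SE − 1.96).

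| r | SE | 95% CI half-width | Power, loss of 1 point | Power, loss of 2 points |
|---|---|---|---|---|
| 0.3 | 0.721 | 1.41 | 28% | 79% |
| 0.5 | 0.609 | 1.19 | 38% | 91% |
| 0.7 | 0.472 | 0.93 | 56% | 99% |
| 0.8 | 0.385 | 0.76 | 74% | 99.9% |
| 0.9 | 0.272 | 0.53 | 96% | >99.9% |

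Unless r is high, losing half of a 2-point effect would often go undetected.

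**5. Responder rule.** The mLK runs from 0 to 12 (5.2.1). Table 1 first schedules mLK scoring at Visit 3, after surgery. From that baseline a participant at 0 can improve by 0 points and one at 1 by at most 1. Neither can reach 2, whatever the treatment does. The documents give no baseline mLK distribution, so the share affected cannot be computed.

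**The case against.** The strongest reply is that H03 is a swapped null and alternative in one line, and that any statistician would run the right test. The linear contrast is named directly before the list, H01 and H02 are its two within-arm parts, and the 3.2 endpoint agrees. The model already yields the week-64 arm difference. The endpoint sits among the other secondary objectives, and 14.10 says the study is not designed to detect differences in secondary outcomes. All of this stands. It limits the point to the wording of H03 and the reporting rule; it does not make the listed null correct.

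A reader might go further and infer that H03 has no identifiable test, and that testing the change or testing the week-64 difference would lead to contradictory findings. The documents do not support that. The text points to the change contrast, and the two tests have different nulls, so they should reject under different truths. If the effect is gone, the change test tends to reject and the week-64 test does not, and both indicate loss. If it is kept, the pattern flips and both indicate persistence. Different reject/retain labels are not opposite conclusions.

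A reader might also infer that a margin or a one-sided test is required. It is not, because the plan makes no claim that a stated amount of effect is retained.

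On the responder rule, the fair reply is that the analysis is exploratory, that an improvement rule does not contradict a worsening threshold, and that Table 1 and 5.2.1 together imply a postoperative baseline. That also stands. A reader might infer that counting improvement generally costs power. This cannot be claimed: it depends on the unknown baseline distribution, and any gain from counting worsening vanishes or reverses at higher baselines.

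**Conclusion.** The point holds as an error of statement in H03. As listed, the null asserts the change it should deny, and the literal decision on its natural contrast is reversed. Nothing elsewhere in the documents corrects it. It should be fixed, but it does not touch the week-52 primary test or the 132 participants.

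The size that matters is the precision of the corrected contrast: a half-width of about 1.2 points at r = 0.5, against a 2-point design effect. A non-significant change is therefore weak evidence of persistence unless r is high. These figures rest on the step 4 assumptions. Two things could move them. Section 14.6 applies Bonferroni without stating the number of tests, and any smaller alpha would widen the interval and lower the power. Assigning the worst score after revision surgery could raise r and is not modelled.

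The responder mismatch is real, minor and separate. It concerns one exploratory analysis, and no general power claim is made.

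**What to change.** In 14.6, restate H03 as: the dupilumab-placebo difference in mLK at week 64 equals that at week 52, tested two-sided. Give the contrast as (T64 − P64) − (T52 − P52), and report its signed estimate with a 95% CI alongside the week-64 arm difference and its 95% CI. Add that a non-significant change will not be read as persistence. If a claim of retaining a stated amount of effect is ever wanted, it would need its own margin.

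In 14.7, name Visit 3 as the baseline. Add the proportion who worsen by 2 or more points at week 52 or have revision surgery before week 52. Keep the improvement proportion as descriptive.

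The cost is SAP wording only. No new data are needed, and the week-52 primary test and sample size do not change.
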